1086 additional troubleshooting

CLINICAL PROTOCOL

- 1087 • Skin reactions from CGM sensor placement or pump infusion set placement that do
1088 not meet criteria for AE reporting

1089 **11.9 Timing of Event Reporting**

- 1090 • UADEs must be reported within 10 working days to the FDA after the sponsor first
1091 receives notice of the adverse effect.

- 1092 • Other reportable adverse events, device malfunctions (with or without an adverse
1093 event) and device complaints should be reported promptly, but there is no formal
1094 required reporting period.

- 1095 • The IDE Sponsor will investigate the UADE and if indicated, report the results of the
1096 investigation to the IRBs, FDA, and MM within 10 working days of the study team
1097 becoming aware of the UADE per 21CFR 812.46(b) (2).

- 1098 • The MM will determine if the UADE presents an unreasonable risk to participants. If
1099 so, the MM must ensure that all investigations, or parts of investigations presenting
1100 that risk, are terminated as soon as possible but no later than 5 working days after the
1101 MM makes this determination and no later than 15 working days after first receipt
1102 notice of the UADE.

- 1103 • In the case of a device system component malfunction (e.g. pump, CGM, control
1104 algorithm), information will be forwarded to the responsible manufacturer by the
1105 study personnel.

1106 **11.10 Stopping Criteria**

1107 **11.10.1 Participant Discontinuation**

1108 Rules for discontinuing study device use are described below:

- 1109 • The investigator believes it is unsafe for the participant to continue on the
1110 intervention. This could be due to the development of a new medical condition or
1111 worsening of an existing condition; or participant behavior contrary to the indications
1112 for use of the device that imposes on the participant's safety

- 1113 • The participant requests that the treatment be stopped

- 1114 • One episode of DKA

- 1115 • One episode of severe hypoglycemia as defined in section 11.2.1.

- 1116 • Development of COVID-19 symptoms or positive COVID-19 test

CLINICAL PROTOCOL

1117 **11.10.2 Suspending/Stopping Overall Study**

1118 In the case of an unanticipated system malfunction resulting in a severe hypoglycemia or severe
1119 hyperglycemia event (as defined in section 11.2), use of the study device system will be
1120 suspended while the problem is diagnosed.

1121 In the event that two distinct episodes of DKA or two distinct severe hypoglycemia events as
1122 defined in section 11.2 occur, the overall study would be suspended while the underlying
1123 conditions are determined.

1124 In addition, study activities could be similarly suspended if the manufacturer of any constituent
1125 study device requires stoppage of device use for safety reasons (e.g., product recall). The affected
1126 study activities may resume if the underlying problem can be corrected by a protocol or system
1127 modification that will not invalidate the results obtained prior to suspension. The study MM will
1128 review all adverse events and adverse device events that are reported during the study and will
1129 review compiled safety data at periodic intervals (generally timed to the review of compiled
1130 safety data by the MM). The MM may request suspension of study activities or stoppage of the
1131 study if deemed necessary based on the totality of safety data available.

1132 **11.11 Independent Safety Oversight**

1133 A MM will review all DKA and severe hypoglycemia irrespective of relatedness to study device
1134 use, and all serious events (including UADEs) related to study device use at the time of
1135 occurrence. The MM can request modifications to the study protocol or suspension or outright
1136 stoppage of the study if deemed necessary based on the totality of safety data available. Details
1137 regarding MM review will be documented in a separate MM document.

1138 **11.12 Definition of a Data Breach**

1139 A data breach is defined in the HITECH Act (43 USC 17932) as an unauthorized acquisition, access,
1140 or use of protected health information (PHI) that compromises the security or privacy of such
1141 information.

1142 **Chapter 12: Miscellaneous Considerations**

1143 **12.1 Prohibited Medications, Treatments, and Procedures**

1144 Participants using glulisine at the time of enrollment will be asked to contact their personal
1145 physician to change their prescribed personal insulin to lispro or aspart for the duration of the
1146 trial.

1147 The study devices (study insulin pump, study CGM) must be removed before Magnetic Resonance
1148 Imaging (MRI), Computed Tomography (CT) or diathermy treatment. Participants may continue
1149 in the trial after temporarily discontinuing use if requiring one of the treatments above.

1150 **12.2 Participant Withdrawal**

1151 Participation in the study is voluntary. Participant may withdraw at any time. For participants
1152 who do withdraw from the study, the study team will determine if their data will be used in
1153 analysis.

1154 **12.3 Confidentiality**

1155 For security and confidentiality purposes, participants will be assigned an identifier that will be
1156 used instead of their name. Protected health information gathered for this study may be shared
1157 with the third-party collaborators. De-identified participant information may also be provided to
1158 collaborators involved in the study after the appropriate research agreement has been executed.

1159 Chapter 13: Statistical Consideration

1160 13.1 Design and Randomization

1161 The study follows a double-blind randomized crossover design, comparing glycemic control
1162 obtained using the UVA HCL system – USS Virginia – alone (control) or in combination with a
1163 smart bolus calculator informed by real-time SI assessments (experimental). All study
1164 participants will undergo both treatment conditions, in different orders, defining two study arms
1165 as shown in Figure 1. Randomization (1:1) will determine whether a participant should undergo
1166 the control or experimental treatment condition first.

1167 13.2 Sample Size

1168 Sample size was determined by power analysis using G*Power 3.1 considering a paired t-test as
1169 the statistical test, comparing control group to experimental group on the primary efficacy
1170 endpoint. Effect size was determined based on the results obtained from the pilot clinical testing
1171 of the SI-informed bolus calculator in open-loop conditions to be $d_z=0.614$. A total sample size of
1172 $N=30$ subjects was obtained considering a 0.66 correlation between groups, 90% power, and
1173 $\alpha=0.05$.

1174 13.3 Outcome Measures

1175 13.3.1 Primary Efficacy Endpoint

1176 The primary endpoint will be the low blood glucose index (LBGI) computed from CGM collected
1177 in the four hours following the dinner meal.

1178 13.3.2 Secondary Outcomes

1179 Secondary endpoints will include analysis over four different time intervals:

- 1180 1. the dinner postprandial period (i.e., the four hours following dinner)
- 1181 2. daytime, i.e., breakfast to bedtime
- 1182 3. nighttime, i.e., bedtime to breakfast
- 1183 4. 24 hours

1184

1185 The glycemic outcomes computed over the four horizons will be:

- 1186 • percentage of time spent below 70 mg/dL
- 1187 • percentage of time spent in 70-140 and 70-180 mg/dL
- 1188 • percentage of time spent above 180 and 250 mg/dL
- 1189 • the high blood glucose index

CLINICAL PROTOCOL

- 1190 • average CGM
- 1191 • CGM coefficient of variation
- 1192 • Total number and amount of carbohydrate administered as rescue treatments

1193 All glycemic outcomes (primary efficacy endpoint and secondary outcomes) will be computed
1194 based on CGM records. The primary analysis will focus on the postprandial period, but other
1195 analyses will evaluate different time intervals to assess whether the impact on the postprandial
1196 period will be influential enough to impact the overall daily control. Paired t-tests or non-
1197 parametric Wilcoxon signed-rank tests will be used to compare the control and experimental
1198 arms on the different glycemic outcomes, in case of normally/non-normally distributed samples
1199 respectively (Shapiro-Wilk test). Significance level will be set at a P value less than 0.05. All
1200 statistical analyses will be computed in SPSS Statistics 26 (IBM).

1201 **13.4 Safety Analyses**

1202 Safety endpoints are secondary outcomes addressing hypoglycemia and hyperglycemia, i.e.,
1203 percentage of time below 70 mg/dL and above 250 mg/dL, and total number and amount of
1204 carbohydrate administered as rescue treatments.

1205 **13.5 Baseline Descriptive Statistics**

1206 Baseline demographic and clinical characteristics of the cohort of all randomized participants will
1207 be summarized in a table using summary statistics appropriate to the distribution of each
1208 variable. Descriptive statistics will be displayed overall and by treatment group.

1209 Will include:

- 1210 • Age
- 1211 • HbA1c
- 1212 • Gender
- 1213 • Race/ethnicity
- 1214 • Diabetes duration
- 1215 • BMI

1216 **13.6 Device Issues**

1217 The following tabulations and analyses will be performed by treatment group to assess device
1218 issues:

- 1219 • Device malfunctions requiring study team contact and other reported device issues

CLINICAL PROTOCOL

- 1220 • Sensor performance metrics (difference, absolute relative difference, and
1221 International Organization for Standardization criteria) – if applicable, by sensor
1222 version.
- 1223 • % time CGM data available - overall and by month
- 1224 The following tabulations will be performed for the Experimental arm only:
- 1225 • Performance metrics, describing the CLC system and its components like:
- 1226 a. % time CGM data were available to the CLC system – overall and by month
- 1227 b. % time in different operational modes per week - overall and by month
- 1228 c. Rate of different failure events and alarms per 48 hours recorded by the CLC
1229 system – overall and by month

1230 **Chapter 14: Data Collection and Monitoring**

1231 **14.1 Case Report Forms and Device Data**

1232 The study data are collected through a combination of case report forms (electronic and paper)
1233 and electronic device data files obtained from the software and individual hardware
1234 components. These electronic device files and electronic CRFs are considered the primary source
1235 documentation.

1236 When data are directly collected in electronic case report forms, this will be considered the
1237 source data. Records will be maintained in accordance with ICH E6 and institutional regulatory
1238 requirements for the protection of confidentiality of participants.

1239 **14.2 Study Records Retention**

1240 Study documents should be retained for a minimum of 2 years after the last approval of a
1241 marketing application in an ICH region and until there are no pending or contemplated marketing
1242 applications in an ICH region or until at least 2 years have elapsed since the formal
1243 discontinuation of clinical development of the investigational product. These documents should
1244 be retained for a longer period, however, if required by local regulations. No records will be
1245 destroyed without the written consent of the sponsor, if applicable. It is the responsibility of the
1246 sponsor to inform the investigator when these documents no longer need to be retained.

1247 **14.3 Protocol Deviations**

1248 A protocol deviation is any noncompliance with the clinical trial protocol, Good Clinical Practices
1249 (GCP), or procedure requirements. The noncompliance may be either on the part of the
1250 participant, the investigator, or the study site staff. As a result of deviations, corrective actions
1251 may be developed by the site and implemented as appropriate. Major deviations will be reported
1252 to the IRB-HSR within 7 calendar days of when the study team becomes aware of the event.

CLINICAL PROTOCOL

1253 **Chapter 15: Ethics/Protection of Human Participants**

1254 **15.1 Ethics Standard**

1255 The investigator will ensure that this study is conducted in full conformity with Regulations for
1256 the Protection of Human Participants of Research codified in 45 CFR Part 46, 21 CFR Part 50, 21
1257 CFR Part 56, and/or the ICH E6.

1258 **15.2 Institutional Review Boards**

1259 The protocol, informed consent form(s), recruitment materials, and all participant materials will
1260 be submitted to the IRB for review and approval. Approval of both the protocol and the consent
1261 form must be obtained before any participant is enrolled. Any amendment to the protocol will
1262 require review and approval by the IRB before the changes are implemented to the study. All
1263 changes to the consent form will be IRB approved; a determination will be made regarding
1264 whether previously consented participants need to be re-consented.

1265 **15.3 Informed Consent Process**

1266 **15.3.1 Consent Procedures and Documentation**

1267 Informed consent is a process that is initiated prior to an individual's agreement to participate in
1268 the study and continues throughout the individual's study participation. Extensive discussion of
1269 risks and possible benefits of participation will be provided. Consent forms will be IRB approved
1270 and the participant will be asked to read and review the document. The investigator or their
1271 delegate will explain the research study to the participant and answer any questions that may
1272 arise. All participants will receive a verbal explanation in terms suited to their comprehension of
1273 the purposes, procedures, and potential risks of the study and of their rights as research
1274 participants. Participant will have the opportunity to carefully review the written consent form
1275 and ask questions prior to signing.

1276 The participant will sign the informed consent document prior to any procedures being done
1277 specifically for the study. A copy of the informed consent document will be given to the
1278 participant for their records. The rights and welfare of the participants will be protected by
1279 emphasizing to them that the quality of their medical care will not be adversely affected if they
1280 decline to participate in this study.

1281 **15.3.2 Participant and Data Confidentiality**

1282 The study monitor, representatives of the IRB or device company supplying study product may
1283 inspect all documents and records required to be maintained by the investigator, including but
1284 not limited to, medical records (office, clinic, or hospital) for the participants in this study.

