 - 328 v. Use of ongoing oral or injectable steroids in the last 8 weeks
- 329 11. Use of an insulin delivery mechanism that is not downloadable by the participant or study
330 team
- 331 12. Known contact with COVID-positive individual within 7 days of any study admission(s)
- 332 13. Symptoms of COVID-19 (e.g., fever, shortness of breath, unexpected loss of taste or smell)
333 developed after taking the mandatory COVID-19 PCR test prior to any study admission(s)
334 or during study admission(s) participation
- 335 14. A positive COVID-19 test within 10 days of any study admission(s)
- 336 15. Not being fully vaccinated at the time of the first camp admission (according to CDC
337 guidelines a person is intended to be fully vaccinated after two weeks from either the
338 second dose of the Pfizer or Moderna vaccine, or the single dose of the Johnson &
339 Johnson vaccine)

340 3.6 Eligibility Screening Procedures

341 The participant will be evaluated for study inclusion and exclusion eligibility after the informed
342 consent form has been signed by the participant and the study team. Individuals who do not
343 initially meet study eligibility requirements may be rescreened at a later date per investigator
344 discretion. The following information will be collected during the screening procedures:

- 345 • Demographics
- 346 • Date of birth
- 347 • Gender

CLINICAL PROTOCOL

- 348 • Race
- 349 • Ethnicity
- 350 • Medical History
- 351 • Duration of disease (number of years)
- 352 • History of insulin pump use and current insulin pump model
- 353 • History of CGM use
- 354 • Current treatment
 - 355 i. Basal rates
 - 356 ii. Carbohydrate ratios
 - 357 iii. Insulin sensitivity factors
 - 358 iv. Target glucose
 - 359 v. Average daily insulin
- 360 • History of diabetic ketoacidosis
- 361 • History of severe hypoglycemia
- 362 • History of seizures
- 363 • Loss of consciousness
- 364 • Surgical history
- 365 • Allergies
- 366 • Concomitant medications
- 367 • Physical Examination – A historical history and physical report within 52 weeks of
- 368 screening appointments may be used if available. Self-reported values are acceptable.
- 369 • Weight and height
- 370 • Blood pressure
- 371 • Pulse
- 372 • Temperature
- 373 • Screening Labs
- 374 • Hemoglobin A1c within past 6 months or average glucose on CGM
- 375 • History of pregnancy or intent to become pregnant during the study
- 376 • COVID-19 vaccination

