377 Screening procedures will last approximately 1-2 hours. Screening can be performed via
378 videoconference. Once all results of the screening evaluations are available, a decision will be
379 made to determine the participant's eligibility for the study or if one or more part of the screening
380 will have to be repeated. If at the first screening or repeat screening an exclusionary condition is
381 identified, the participant will be excluded from participation with follow up and referred to their

CLINICAL PROTOCOL

382 primary care physician as needed. The study physician may elect to rescreen participants if their
383 clinical situation changes.

384 **Chapter 4: Randomization Visit**

385 Once eligibility is met, the participant may continue with randomization at the conclusion of the
386 screening appointment. Using a randomized block design, the participants will be randomly
387 assigned to either one of the two treatment groups. Screening failures and study dropout
388 participants may be replaced.

389 **4.1 Pilot Participants**

390 Participants will not be randomized in the Pilot Study.

391 **4.2 Main Study Participants**

392 Approximately 30 participants will be randomized 1:1 to use USS Virginia or USS Virginia with SI-
393 informed bolus calculator first. Up to 70 participants may sign the informed consent form.

394 **Chapter 5: Study Equipment Training**

395 Participants will be trained on the use of the study CGM after study eligibility has been met.
396 Additional equipment training may begin at arrival to study admission(s) after the system
397 equipment has been put in place. The purpose of this training is to introduce the study insulin
398 pump and study CGM to the participant.

399 **5.1 CGM Training**

400 A study CGM will be provided to all participants after meeting study eligibility. The participants
401 will be provided with CGM equipment and instructed to place the study CGM ~24-48 hours prior
402 to arrival to camp and use the study CGM on a daily basis. If the participant has prior use of the
403 CGM, re-training will be specific to the individual. The study team will have participants who are
404 not familiar with the study CGM watch the Dexcom online training videos
405 (<https://www.dexcom.com/training-videos>). Study staff will specifically identify how alarms are
406 set using the app and the frequency that these alarms repeat. Parents may optionally use the

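### A participant stopped for severe hypoglycemia on the first system has no LBGI pair, drops out of the primary paired test and may be replaced by a completer

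*Combined protocol and SAP*

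**What the plan says.** All of the following is in the combined protocol and SAP.

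- **Replacement.** Chapter 4 says that "Screening failures and study dropout" participants may be replaced. It makes no exception by reason. Sections 1.4.1 and 3.1 set the goal as about 30 participants completing.
- **Stopping.** Section 11.10.1 lists "One episode of severe hypoglycemia as defined in section 11.2.1" among the rules that end study device use. Nothing provides for that participant to resume.
- **Sequence.** Under sections 1.3 and 8.4.4 each participant uses one system and then the other, changing before breakfast on Day 3 of the weeklong camp or at the second weekend.
- **Endpoint and test.** The primary endpoint (13.3.1) is CGM-based LBGI in the four hours after dinner. Under 13.3.2 paired t-tests or non-"parametric Wilcoxon signed-rank tests will be used to compare the control and experimental" arms, according to a Shapiro-Wilk result.
- **Populations and missing data.** The set of all randomized participants is named only for the baseline table (13.5). No analysis set or missing-data rule is given for the outcomes. Section 12.2 leaves the use of withdrawn participants' data to the study team.
- **Safety outcomes.** Section 13.4 lists time below 70 mg/dL, time above 250 mg/dL and rescue carbohydrate. It does not list severe hypoglycemia or DKA by system. The Medical Monitor reviews each such event (7.3, 11.11).

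**The concern.** Each rule is reasonable by itself. Together they make membership of the primary comparison depend on the kind of outcome being compared. A severe low on the first system ends device use, no second-system LBGI is collected, the paired test cannot use the single value, and a completer may fill the place. The 30 analysed pairs are then completers by selection.

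If the experimental system contributed to the event (section 1.1 lets it raise a bolus to 130% of the standard dose), the primary result loses an unfavourable observation. If the control system contributed, the primary result loses evidence of benefit. The discretion in 12.2 does not solve this: even if the team decides to use the data, a paired test has no place for a participant with one period.

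**Working it through.** **1. The plan's own figure.** Inputs from 13.2: paired t-test, dz = 0.614, "0.66 correlation between groups, 90% power", alpha 0.05. With the exact noncentral t distribution and a two-sided test, the smallest n with at least 90% power is 30 (power 90.1%). The plan's N reproduces. The correlation is not needed once dz is given.

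**2. Loss without replacement.** The same formula gives 89.1% power with 29 pairs and 87.9% with 28. Lost precision is not the issue. Replacement restores 90.1% but leaves the selection in place.

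**3. How likely is an event?** The documents give no rate. If each of 30 participants has an assumed first-period probability p, the chance of at least one event is 1 − (1 − p)^30:

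| p (assumed) | Expected events | Chance of at least one |
|---|---|---|
| 1% | 0.3 | 26% |
| 2% | 0.6 | 45% |
| 5% | 1.5 | 79% |

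**4. Effect on the mean difference.** Measure in SDs of the paired differences, with the planned mean at 0.614 in favour of the experimental system. Suppose the lost pair would have been k SD in the wrong direction and its replacement is an average pair. The mean of 30 then moves by (0.614 + k)/30:

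| k (assumed) | Shift (SD) | Share of 0.614 |
|---|---|---|
| 0 | 0.614/30 = 0.020 | 3% |
| 1 | 1.614/30 = 0.054 | 9% |
| 2 | 2.614/30 = 0.087 | 14% |
| 3 | 3.614/30 = 0.120 | 20% |

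**5. A milder model.** Take bivariate normal outcomes with correlation 0.66 and drop the participants with the highest first-period values.

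- With no true effect and equal stopping on both systems, the bias is about zero.
- With no true effect and about 1 in 30 lost, all from the sequence starting on the experimental system, the mean shifts by about 0.03 SD in its favour. It shifts by about the same amount the other way if all losses start on control.
- With a true dz of 0.614, a common stopping threshold and 1% to 7% loss, the mean difference is 0.59 to 0.61.

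**6. Worst-rank analysis.** Simulate 30 participants with normal differences and dz = 0.614. Give each stopped participant the most extreme rank against the system in use, then apply a two-sided signed-rank test at 0.05:

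| Events | Chance of a positive result |
|---|---|
| None | about 89% |
| One on experimental | about 75% |
| Two on experimental | about 51% |
| One on control | about 92% |
| One on each | about 82% |

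This is a different estimand, a composite of LBGI and the stopping event. The table shows how far the conclusion can depend on how one or two people are handled. It does not measure bias in the LBGI estimate.

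**The case against.** The strongest reply is that the exposure is small and the events are not concealed. Severe hypoglycemia here requires altered consciousness or cognitive impairment (11.2.1), in a camp with continuous remote CGM monitoring and overnight staff (8.4.1). It may not occur at all. If it does, it is a reportable event (11.2) that goes to the Medical Monitor. Replacement is permitted, not required. Section 11.10.1 stops device use without calling that person a dropout, and Chapter 4 does not say that anyone's data are deleted. A severe low overnight or during morning activity would also lie outside the four post-dinner hours. All of this stands, and it limits the size. It does not restore the missing pair, and Medical Monitor review is not a comparison between systems.

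Four stronger readings are tempting, and the documents do not support them.

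- **That the primary comparison includes only people without the event.** A participant whose event comes on the second system, after a dinner there, still has LBGI on both systems. Only first-system stops remove the pair by this route.
- **That DKA belongs in the same argument.** A DKA stop also breaks a pair, but DKA is not hypoglycemia. Giving it the worst rank on a low-glucose index would score it wrongly.
- **That exclusion criterion 13, which can be met "or during study admission(s) participation", is part of the same mechanism.** It concerns COVID-19 symptoms, has no link to hypoglycemia, and is already covered as a discontinuation rule in 11.10.1.
- **That 11.10.2 caps stops at two.** It suspends the study after two DKA episodes or two severe hypoglycemia events, counts the two types separately, and foresees that study activities may resume after a suspension.

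**Conclusion.** The point holds for severe hypoglycemia on the first system before any second-system dinner. The stated rules then remove the participant from a hypoglycemia endpoint because of hypoglycemia, and they allow a completer to take the place. The bias can run in either direction.

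The size is conditional on an event, and the documents give no rate. For one replaced pair it is 0.02 to 0.12 SD of the differences (3% to 20% of the planned effect), resting on the assumed 0 to 3 SD range. The milder model gives about 0.03 SD when all losses fall in one sequence. A reader might infer from the 75% and 51% figures that the planned test is biased by that much. They compare a composite with LBGI and show only events on the experimental system, so they do not support that. N=30 is not in question. This is a cheap improvement, best made before outcome data exist.

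**What to change.** 1. **Chapter 4.** Limit replacement to people who leave before connection to a study system (8.3.2). More participants may be added to reach 30 completers, but everyone who was connected stays in the reported cohort and their data are kept.
2. **Section 13.3.** Keep the paired test as primary. Prespecify a signed-rank sensitivity analysis in which a participant stopped for severe hypoglycemia before providing a pair takes the worst rank against the system in use. A mixed model with participant as a random effect, using the dinners of one-system participants, is an optional further sensitivity analysis. It would not by itself correct loss triggered by the outcome.
3. **Section 13.4.** Tabulate severe hypoglycemia, DKA, discontinuations and replacements by system and sequence. DKA stops are reported there and do not take the worst LBGI rank.

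The clinical stopping rule and N=30 stay as they are. The cost is a few sentences, one table and one extra analysis. The result may look slightly less favourable if an event falls on the experimental system.
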